## 4. TREATMENTS

### 4.1 TREATMENTS TO BE ADMINISTERED

Patients will receive Xentuzumab (BI 836845) weekly in combination with afatinib once daily. The manufacturers for each of the products are listed in Section 4.1.1.

#### 4.1.1 Identity of BI investigational product and comparator product

##### 4.1.1.1 Xentuzumab (BI 836845) (investigational product)

Substance:	Xentuzumab (BI 836845) human monoclonal antibody
Pharmaceutical form:	Liquid formulation
Source:	Boehringer Ingelheim Pharma GmbH & Co. KG
Unit strength:	10 mg/ml of Xentuzumab (BI 836845) supplied in 20 ml vials (200 mg/vial)
Weekly dose:	1000 mg (starting dose), 750 mg
Posology:	Once weekly administrated through one hour intravenous infusion. Infusion duration may be extended to over one hour and up to a maximum of three hours in cases of grade $\geq 2$ infusion reactions. See Section 4.1.3 for dose selection
Route of administration:	Intravenous infusion. Appropriate dose of Xentuzumab (BI 836845) will be diluted in isotonic sodium chloride solution (0.9%)
Duration of use:	Continuous weekly dosing (days 1, 8, 15 and 22 in a 28-day course) in the absence of disease progression, intolerable AEs or other reason necessitating withdrawal

##### 4.1.1.2 Afatinib (investigational product)

Substance:	Afatinib
Brand name:	Giotrif
Pharmaceutical form:	Film-coated tablet
Source:	Boehringer Ingelheim Pharma GmbH & Co. KG
Unit strength:	20 mg, 30 mg or 40 mg (the dose of afatinib in tablets is related to the free base equivalent of afatinib)

Proprietary confidential information.

© 2016 Boehringer Ingelheim International GmbH or one or more of its affiliated companies. All rights reserved.  
This document may not - in full or in part - be passed on, reproduced, published or otherwise used without prior written permission.

Route of administration:	Oral
Posology:	Once daily. Take afatinib at least 1 hour before or 3 hours after a meal. See Section 4.1.3 for dose selection
Duration of use:	Continuous daily dosing until criterion in Section 3.3.4.1 is met

## 4.1.2 Method of assigning patients to treatment groups

### 4.1.2.1 The dose confirmation Part A

Treatment slots are assigned by the BI Clinical Monitor (CM) in close communication (email/phone/FAX) with the recruiting sites and will be assigned on a competitive basis. After the BI Clinical Monitor has been notified by a site about a potential patient, the slot will be reserved to this site for a maximum of seven calendar days. If the informed consent form (ICF) has not been signed by the potential patient within this time window, the slot will be opened up again for all recruiting sites.

Patients that meet the eligibility criteria and who have given their written informed consent will be entered into the study.

Before entering patients at the next dose level it will be ensured that all patients at an ongoing cohort have completed the first course. Prior to inclusion of a new patient, the investigator should confirm the respective dose with the BI clinical monitor.

### 4.1.2.2 The expansion Part B

The enrolment in Part B is competitive. In order to reach an adequate number, eligible patients need to be communicated to the BI Clinical Monitor (CM). These communications may be done by FAX/e-mail and will be documented. Patients that meet the eligibility criteria and who have given their written informed consent will be entered into the Part B of the study. Investigators will be notified by the sponsor when the appropriate number of patients have been screened and screening is complete, thereafter additional patients will not be allowed to recruit for this study. Patients who have signed an informed consent form and are eligible prior to notification of the termination of recruitment will be allowed to participate in the study.

## 4.1.3 Selection of doses in the trial

### 4.1.3.1 Planned dose levels in the Part A

The Part A will follow an escalation/de-escalation “3+3” design. The starting dose level consists of 1000 mg weekly Xentuzumab (BI 836845) in combination with 30mg/day of afatinib.

The approved dose of afatinib in first-line monotherapy treatment of EGFR mutant NSCLC is 40 mg daily. Afatinib has also been studied in NSCLC with settings of EGFR TKI failure. In the LUX-Lung 1 study, afatinib was administered as monotherapy with a daily dose of 50 mg ([P12-03682](#)). Afatinib at 40 mg daily in combination with bi-weekly cetuximab of 500 mg/m^2 has been established as recommended dose for patients who failed prior EGFR TKI ([P12-11350](#)). In the current trial, an afatinib dose of 30 mg daily, a dose lower than the registered dose, has been chosen as a starting dose level. Given the cross-talk between IGF-1R and EGFR, it is conceivable that side-effects as well as efficacy of EGFR TKIs might be potentiated when an IGF pathway inhibitor is added ([R16-4930](#), [R12-5650](#)). Hence, to mitigate this risk, a lower than labeled dose is chosen for the first dose cohort.

The starting dose level of Xentuzumab (BI 836845) has been determined as 1000 mg every week. Based on data from two phase I studies, the recommended monotherapy dose of Xentuzumab (BI 836845) is 1000 mg every week. In these two studies, a formal MTD was not established in the absence of DLT from 1000 mg per week up to 1800 mg per week. About 90% neutralization of IGF-1 can be achieved with dose of 1000 mg every week. Tolerability and safety are considered favourable even at dose levels above 1000 mg every week. Therefore, a dose of 1000 mg Xentuzumab (BI 836845) every week is chosen as starting dose to combine with 30 mg QD of afatinib.

Table 4.1.3.1: 1 Planned dose levels

Dose level	Xentuzumab (BI 836845) (mg/week)	Afatinib (mg /day)
Dose level -1	750	30
Dose level 1	Starting dose	30
Dose level 2	Intended RP2D	40

Study treatment will be administered in 4-week (28 days) courses.

To determine the maximum tolerated dose (MTD), patients will be entered sequentially into escalating/de-escalating dosage tiers of BI836845 and afatinib (see Table 4.1.3.1: 1). Three patients will be treated at the starting dose level (dose level 1). If 1 out of 3 patients at that dose level experiences a dose limiting toxicity (DLT), then 3 additional patients will be treated at that dose level. If more than 1 out of 3 or more than 1 out of 6 patients at dose level 1 have a DLT, then the MTD has been exceeded and the dose is de-escalated to dose level -1. If 1 out of 3 patients experience a DLT at any dose level, then 3 additional patients will be treated at that dose level. If at dose level 1, 0 out of 3 patients or 1 out of 6 experiences a DLT, the dose will be escalated to dose level 2. If 0 or 1 out of 3 patients experience a DLT and dose level 2, then 3 additional patients will be treated at that dose level. If more than 1 out of up to 6 patients experiences a DLT at the lowest dose level -1, the trial will be discontinued, and no MTD could be established. Intra-patient dose escalation is not permitted.

For decision on dose escalation, please see [Section 3.1.1](#). During the dose confirmation stage (Part A) of the study, the safety profile as well as DLTs will be discussed with the

investigator as well as a coordinating investigator. The decision on the next dose level or determination of the MTD will be documented.

Table 4.1.3.1: 2 Rules for dose escalation/de-escalation

Number of Patients with DLT at a Given Dose Level	Escalation/de-escalation Decision Rule
0 out of 3	Enter 3 patients at the next dose level.
$\geq 2$ out of 3	Dose de-escalation will commence. Three (3) additional patients will be entered at the lower dose level.
1 out of 3	Enter up to 3 more patients at this dose level. If 0 of these 3 additional patients experience DLT, proceed to next dose level. If 1 or more of these 3 additional patients experience DLT, then dose de-escalation will commence.
$\leq 1$ out of 6 at the highest dose level	This is the MTD (or maximal administered dose) to be considered as RP2D

#### 4.1.3.2 Part B – dosing schedule

The decision on dose escalation/de-escalation, MTD and RP2D will be determined in discussion with a group of BI Trial Clinical Monitor, BI project physician (TMM) and investigators including Coordinating Investigator and taking into account patient safety. This decision will be documented and patients will be treated at the MTD/RP2D determined from Part A. For decision on MTD/RP2D determination, please see [Section 3.1.1](#).

MTD/RP2D has been determined as Xentuzumab (BI 836845) 1000 mg/week plus afatinib 40 mg/day and it will be used as starting dose in Part B. However, in part B, for patients who had disease progression while on afatinib less than 40 mg/day, the starting dose is the last dose of afatinib. Alternative starting dose of afatinib must be discussed and agreed by Sponsor.

#### 4.1.4 Drug assignment and administration of doses for each patient

The treatment medication assignment for Xentuzumab (BI 836845) and afatinib will be managed through an IRT system. In addition, patient's screening, dose assignment, all drug dispensation visits and EOTV will be collected in the IRT system.

##### 4.1.4.1 Initial study drug assignment and administration

General information that applies to this study regardless of the IRT is described in below sections of each individual study drug. The medication kit as well as the treatment will be assigned with the support of the IRT system. The detailed information regarding handling of medication number will be described in ISF.

Proprietary confidential information.

© 2016 Boehringer Ingelheim International GmbH or one or more of its affiliated companies. All rights reserved.  
This document may not - in full or in part - be passed on, reproduced, published or otherwise used without prior written permission.

Before entering patients at the next dose level of Part A, it will be ensured that all patients at the current ongoing dose level have completed at least one course of treatment.

#### 4.1.4.1.1 Xentuzumab (BI 836845)

Patients will start treatment with their assigned dose tier (see [Section 4.1.3](#)) or RP2D of Xentuzumab (BI 836845) from course 1 day 1. Xentuzumab (BI 836845) will be administered at the investigator site intravenously over one hour with a constant infusion rate on the treatment day as specified in the [Flow Chart](#). No prophylaxis for infusion-related reaction is recommended at Course 1 Visit 1. Mannitol is used in the formulation of Xentuzumab (BI 836845), so an infusion duration of less than one hour must be avoided. The infusion time may be extended to over one hour and up to a maximum of three hours in cases of CTCAE grade  $\geq 2$  infusion reactions (see [Section 4.2.3.4](#) for grading and management of infusion reactions). Further information on infusion equipment and procedure is described in the ISF. In case of a delay or an interruption of infusion, the reason and the exact time of deviation must be recorded in the eCRF. The accuracy of this information is crucial for the proper evaluation and appraisal of the pharmacokinetics and other data.

Detailed information of dispensation, preparation, and handling of Xentuzumab (BI 836845) will be described in ISF.

#### 4.1.4.1.2 Afatinib

Patients will take a single oral dose of afatinib each day starting at their assigned dose-level (Part A) or RP2D (Part B), continuously during each treatment course. The medication should be taken at the same time each day ( $\pm 2$  hours) without food (at least one hour before or at least three hours after a meal) to ensure a dose interval of approximately 24 hours.

If a dose is missed, it should be taken within the same day as soon as the patient remembers. However, if the next scheduled dose is due within 8 hours then the missed dose must be skipped and the next scheduled dose at the usual time should be taken. Patients with emesis must not take a replacement dose.

The tablet should be swallowed with a glass of water (approximately 250 mL). Afatinib tablets should not be chewed or crushed, but may be administered after dispersing the afatinib tablets according to the following procedure: If dosing of whole tablets is not possible, afatinib tablets can also be dispersed in approximately 100 ml of non-carbonated drinking water. No other liquids should be used. The tablet should be dropped in the water, without crushing it, and occasionally stirred for up to 15 min until the tablet is broken up into very small particles. The dispersion should be drunk immediately. The glass should be rinsed with approximately 100 ml of water which should also be drunk. The dispersion can also be administered through a naso-gastric tube.

Medication will be dispensed in bottles containing 30 tablets at the beginning of each treatment course. Treatment will start when the patient is taking the first dose of medication at course 1 Day1. Study drug will be prescribed by the investigator and may be dispensed either by the investigator, site staff or affiliated pharmacy.

Proprietary confidential information.

© 2016 Boehringer Ingelheim International GmbH or one or more of its affiliated companies. All rights reserved.

This document may not - in full or in part - be passed on, reproduced, published or otherwise used without prior written permission.

#### 4.1.4.2 Additional course of treatment

The doses of Xentuzumab (BI 836845) and afatinib assigned upon entry to this trial will be used on all scheduled administrations described in the [Flow Chart](#) unless the patient experiences DLTs or treatment related adverse events which require dose modification.

Intra-patient dose escalation of either afatinib or BI 836345 is not allowed in this trial.

Patients demonstrating a clinical benefit (i.e., with either an objective tumour response or the absence of disease progression) with the trial drug, and who have recovered from any clinically relevant drug-related AE, are eligible for further treatment courses as per the [Flow Chart](#) until any of the conditions in [Section 3.3.4.1](#) is met.

#### 4.1.4.3 Temporary treatment interruption and dose reduction

DLTs or those AEs requiring dose adjustment as indicated within the prescribing information, should be managed by treatment interruptions and subsequent dose reductions of the presumed causal study drug(s) according to the schedule described in [Table 4.1.4.3: 1](#). Please also refer to Section 4.2.3 for additional recommendations. In Part A, both Xentuzumab (BI 836845) and afatinib must be paused when a DLT occurs during the first treatment course. Dose reductions will apply to individual patients only and dose of Xentuzumab (BI 836845) and/or afatinib may be reduced independent of one another. Once the dose has been reduced, it cannot be increased later.

To prevent the development of more severe adverse events, treatment related AEs should be closely monitored and managed early and proactively as described in [Section 4.2.3](#).

Treatment should be paused until a patient has recovered from a drug-related AE to grade  $\leq 1$  or baseline. Baseline is defined as the CTCAE grade at the start of treatment. For patients who develop a DLT, treatment may be resumed at reduced dose according to the dose reduction scheme of the patient's starting dosage (Table 4.1.4.3: 1). If a patient has not recovered to Grade  $\leq 1$  or baseline within 14 days, study treatment must be permanently discontinued. In the event that the patient is deriving obvious clinical benefit according to the investigator's judgment, further treatment with study drug(s) will be decided in agreement between the sponsor and the investigator.

Diarrhoea and skin-related AEs are common side-effects of afatinib listed within the prescribing information. Please refer to the current afatinib prescribing information/SmPC for dose adjustment recommendations (except for the Course 1 of Part A if a DLT occurs, in which case both drugs need to be interrupted until AE recovery, refer to [Section 5.2.6](#)). When these AEs occur and are considered related to study treatment, the first dose modification is recommended to be made preferentially for afatinib.

In the event of any unrelated AEs or related non-DLT AEs, the investigator may choose to interrupt the medication (Xentuzumab (BI 836845) and/or afatinib) for up to 14 days, but no dose reduction should occur unless indicated in the current drug label/SmPC of afatinib. If the medication is interrupted for more than 14 days, the decision to continue with

Proprietary confidential information.

© 2016 Boehringer Ingelheim International GmbH or one or more of its affiliated companies. All rights reserved.  
This document may not - in full or in part - be passed on, reproduced, published or otherwise used without prior written permission.

Xentuzumab (BI 836845) and/or afatinib will be made by the BI clinical monitor in agreement with the investigator.

Applicable dose levels for weekly Xentuzumab (BI 836845) are 1000 mg and 750 mg. For afatinib, the applicable dose levels are 40 mg, 30 mg, and 20 mg. No dose reduction is allowed below 750 mg for Xentuzumab (BI 836845) or below 20 mg for afatinib. Patients who need further dose reduction which is not allowed according to protocol should be discontinued from that drug treatment. An exception to this rule can be considered upon discussion with BI's Clinical Monitor in patients who derive obvious clinical benefit according to the investigator's judgement. Alternative dose modification scheme can only be considered after discussion and agreement between the investigator and the BI clinical monitor.

Management of afatinib related adverse reaction and dose adjustment should be based on the European SPC or current prescribing information for afatinib of the respective country or institutional standard if not specified by protocol.

During temporary treatment interruption of Xentuzumab (BI 836845), the scheduled drug infusion will be skipped and will not be retrospectively administered.

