Drug-related DLTs (see Section 5.2.6 ) or any other drug-related AE $\geq 3$ 	
Pause afatinib and/or Xentuzumab (BI 836845) treatment until patient has recovered to Grade <math>\leq 1</math> or baseline1. In Part A, both afatinib and Xentuzumab (BI 836845) must be paused when DLT occurs in the first course.
 
Resume treatment at reduced dose according to schedule opposite. Drug without interruption will maintain dose level.
 
If patient has not recovered to Grade <math>\leq 1</math> or baseline within 14 days study treatment must be permanently discontinued.
	
Afatinib (if interrupted)
 
If patient was receiving 40 mg, resume treatment at a dose of 30 mg.
 
If patient was receiving 30 mg, resume treatment at a dose of 20 mg.
 
If patient was receiving 20 mg, discontinue afatinib.
 
Xentuzumab (BI 836845) (if interrupted)
 
Reduce Xentuzumab (BI 836845) by not more than one level at a time. (1000mg (starting dose)->750mg (-1 dose level))
 
If patient need further dose reduction below 750 mg, discontinue BI836845.

Proprietary confidential information.

© 2016 Boehringer Ingelheim International GmbH or one or more of its affiliated companies. All rights reserved.

This document may not - in full or in part - be passed on, reproduced, published or otherwise used without prior written permission.

Table 4.1.4.3: 1 Dose reduction scheme by AE type and CTCAE Grade (Part A and Part B) (Cont'd)

AE type and CTCAE Grade	Action	Dose reduction scheme
Acute onset and/or unexplained worsening of pulmonary systems (dyspnoea, cough, fever)	Pause afatinib and Xentuzumab (BI 836845) while clinical assessment to exclude ILD is completed.	If ILD is ruled out as a cause of symptoms, grade symptoms and relatedness and report as AEs. If AEs are not drug-related, resume afatinib and Xentuzumab (BI 836845) at current dose. If AEs are drug-related, follow directions in row above.  If ILD is confirmed, discontinue afatinib and Xentuzumab (BI 836845).
Xentuzumab (BI 836845) induced CTCAE grade $\geq 3$ infusion-related reaction	No action on afatinib  Pause BI836845	See specific guideline in Section 4.2.3.4

 Baseline is defined as the CTCAE Grade at the start of treatment

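### Section 4.1.4.3 gives two xentuzumab doses for resuming after a related Grade 3 or higher AE that is not a DLT: 1000 mg in the text, 750 mg in the table

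*Protocol*

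**What the plan says.** Protocol Section 4.1.4.3 sets the dose-modification rules in running text and in Table 4.1.4.3: 1, whose title covers Parts A and B.

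**Text.** The opening sentence sends to the table's reduction schedule only "DLTs or those AEs requiring dose adjustment as indicated within the prescribing information". A later paragraph deals with the remaining events: "In the event of any unrelated AEs or related non-DLT AEs, the investigator may choose to interrupt the medication" (either drug, up to 14 days), "but no dose reduction should occur unless indicated in the current drug label/SmPC of afatinib". The section also states: "Once the dose has been reduced, it cannot be increased later".

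**Table, row 2.** The row covers DLTs "or any other drug-related AE" of Grade 3 or higher. Footnote 3 exempts alopecia, infusion reaction and allergic reaction. The instruction is to pause one or both drugs until recovery, then: "Resume treatment at reduced dose according to schedule opposite. Drug without interruption will maintain dose level". For xentuzumab, if it was interrupted: "Reduce Xentuzumab (BI 836845) by not more than one level at a time", with the step given as 1000 to 750 mg. Without recovery to Grade 1 or baseline within 14 days, treatment stops permanently, subject to a clinical-benefit exception.

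**Table, row 3.** Acute pulmonary symptoms require both drugs to be paused while ILD is excluded. If ILD is ruled out and the event is drug-related, the site is referred back to row 2.

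**Note under the table.** Here the bar on dose reduction is limited to unrelated events. Related non-DLT events are not mentioned.

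**The concern.** The same event can fall under a rule that forbids reducing xentuzumab and a rule that requires it. The text's only exception is the afatinib label, which does not set a xentuzumab dose.

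Two things are at stake. The first is patient management: after a severe related toxicity, the re-exposure dose depends on which part of Section 4.1.4.3 the site follows, and a reduction is permanent. The second is the meaning of the exposure data. SAP Section 5.4.2 reports patients with a xentuzumab dose reduction, time to first reduction and dose intensity, and all three would mix two rules. SAP Table 6.2:1, code C2, counts failure to follow the Section 4.1.4.3 reduction scheme as a potentially important protocol violation. For these events either action breaches one of the two rules, so the code cannot be applied consistently.

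**Working it through.** The plan gives no figure to reproduce. The check compares the two rules and then sizes the effect.

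**1. Do the rules overlap?** They do if some related Grade 3 or higher events are not DLTs. By the listed criteria in Section 5.2.6, these are not:
- Grade 3 hyperglycaemia lasting 48 hours or less;
- Grade 3 fatigue lasting seven days or less;
- Grade 4 neutropenia lasting under seven days;
- any other non-haematologic event of Grade 3 or higher with an interruption of 14 days or less.

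All are drug-related events of Grade 3 or higher, so row 2 applies. All are non-DLT, so the text's bar applies, unless the investigators and sponsor qualify the event as a DLT under the discretionary clause that ends the list.

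**2. The residual non-haematologic class.** The listed DLT criterion needs an interruption of more than 14 days. Row 2 ends treatment when there is no recovery within 14 days. The two clocks are not worded identically, but broadly:
- recovery within 14 days: not a listed DLT; the table resumes at a reduced dose and the text bars the reduction;
- no recovery within 14 days: a listed DLT; the table discontinues.

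Apart from the clinical-benefit exception and the discretionary clause, the patients in this class who resume are the non-DLT patients, so the table's reduction falls on those the text protects from it.

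**3. Worked case.** A related Grade 3 non-haematologic event, not otherwise listed as a DLT, recovers after a 10-day xentuzumab pause. The text gives 1000 mg on resumption. Row 2 gives 750 mg.

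**4. Afatinib.** The text's exception may reconcile the two rules for afatinib. The label is not in the documents, so no conflict is claimed there.

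**5. Size for one patient.** SAP Section 5.4.2 defines xentuzumab dose intensity as

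100 × total dose received ÷ (planned dose per infusion × number of visits with an infusion).

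Skipped infusions are not in the denominator, so only 750 against 1000 mg matters. The infusion counts and timing below are assumptions.

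| Infusions given | Reduced from infusion 5 | Reduced from infusion 2 | Not reduced |
|---|---|---|---|
| 8 | (4×1000 + 4×750)/8000 = 87.5% | (1000 + 7×750)/8000 = 78.1% | 100% |
| 12 | (4×1000 + 8×750)/12000 = 83.3% | (1000 + 11×750)/12000 = 77.1% | 100% |
| 24 | (4×1000 + 20×750)/24000 = 79.2% | (1000 + 23×750)/24000 = 76.0% | 100% |

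**6. Size for Part B.** With 18 patients (Protocol Section 7.6), the proportion with at least one xentuzumab reduction moves by 1/18 = 5.6 points for one affected patient, 2/18 = 11.1 for two and 3/18 = 16.7 for three.

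**The case against.** The best reply is that the table is plainly meant to govern. The note under it limits the bar to unrelated events, and the Amendment 2 rationale for the table change points the same way. Section 4.1.4.2 also allows dose changes for treatment-related events that require them, not only for DLTs. On this reading, one phrase was left un-updated. The intent is probably as described, but no passage gives the table precedence. Section 4.1.4.2 leaves open which events require a change, and the opening sentence of Section 4.1.4.3 leans the other way.

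Second, the overlap is limited. Row 2 cuts xentuzumab only if it was paused, and infusions are weekly, so a short event may pass without a missed dose. This stands in part, and no event rate is given. But the DLT durations count time at Grade 3 or higher, whereas the pause lasts until Grade 1 or baseline, so an infusion can still be missed. Row 3 also makes the pause of both drugs mandatory, although the table does not say whether a diagnostic hold counts as an interruption under row 2.

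Third, controls exist: regular sponsor–investigator teleconferences (Section 3.1.1), review of violations, and "Alternative dose modification scheme can only be considered after discussion and agreement between the investigator and the BI clinical monitor". These help only if someone sees a question to raise. A site following either written rule would not think it was using an alternative scheme.

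Fourth, the analyses are descriptive, code C2 excludes no patient, and Section 4.1.3.1 reports good monotherapy tolerability above 1000 mg weekly. All true, and this limits the weight of the point. It does not settle which dose to give after a severe related event on the combination.

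**Conclusion.** The concern holds. For related events of Grade 3 or higher that are not DLTs, with xentuzumab paused, Section 4.1.4.3 prescribes both 1000 mg and 750 mg and does not say which applies. The difference is 25% of every later infusion and is irreversible for the patient. Dose intensity would be 76.0% to 87.5% rather than 100% under the assumed infusion counts, and the Part B reduction proportion moves by 5.6 points per affected patient.

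The number of affected patients cannot be estimated. The documents give no rate for such events on the combination, and Section 2.3 says most monotherapy events were Grade 1 or 2. The definitions of DLT and objective response are untouched. The finding rests on the protocol as revised on 02 Nov 2016. SAP Section 7 refers to a protocol amendment 4, whose text is not available here and could have altered this paragraph. The point should be corrected, but it does not threaten the trial's primary conclusions.

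**What to change.** Let Table 4.1.4.3: 1 govern, by two edits to the text of Section 4.1.4.3:

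1. In the paragraph on unrelated and related non-DLT events, replace the reference to related non-DLT AEs with *related AEs not listed in Table 4.1.4.3: 1*.
2. In the opening sentence, after the mention of the prescribing information, add *or AEs listed in Table 4.1.4.3: 1*.

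The first edit removes the bar. The second brings the row 2 events within the text's reference to the table. The section's separate sentence that patients with a DLT may resume at a reduced dose can stay, since it is permissive and contradicts nothing.

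The cost is two phrases, a clarification letter to sites until the change takes effect, and the ethics committee and authority approvals that Section 8.1 requires for amendments. No SAP change, new data or new procedure is needed.
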